### *Dosages*

All volunteers will be instructed to take their last meal 6 hours before start of the breath test.

Volunteers in the  $^{13}\text{C}$ -butyrate group receive an oral dose of  $0.03 \mu\text{mol } ^{13}\text{C}$ -butyrate(10).

Volunteers in the  $^{13}\text{C}$ -glucose group receive an oral dose of  $20 \text{ mmol } ^{13}\text{C}$ -glucose(16).

### *Follow-up*

There is no follow-up of healthy volunteers.

## **4. STUDY POPULATION**

### **a. Population (base)**

Healthy volunteers with no gastrointestinal complains and unremarkable medical history will be asked to participate in our study through information folders.

### **b. Inclusion criteria**

In order to be eligible to participate in this study, a subject must meet all of the following criteria:

- $\geq 18$  years of age
- Experience with cycling
- Signed informed consent
- Unremarkable medical history (no gastrointestinal diseases, no cardiac or pulmonary diseases)
- No gastrointestinal complaints

### **c. Exclusion criteria**

A potential subject who meets any of the following criteria will be excluded from participation in this study:

- Unable to sign informed consent
- Pregnancy

### **d. Sample size calculation**

This study is a proof of principal study, no previous studies exist on this topic, therefore a sample size calculation could not be performed. We have chosen to include a total of 20 healthy volunteers in order to be able to compare 5 control subjects and 5 intervention

subjects for each breath test. In case the number of 5 subjects per group is insufficient to detect a statistical difference, the generated data can be used to perform a sample size calculation for a second study.

## 5. TREATMENT OF SUBJECTS

### 5.1 Investigational product/treatment

#### *Intervention*

Two different intervention groups both consisting of 5 volunteers will be used during the study. The first group will receive  $^{13}\text{C}$ -butyrate and the second group  $^{13}\text{C}$ -glucose. Both intervention groups will be performing a standardized bicycle ergometer exercise test with a total duration of 30 minutes(12). The exercise test has been proven to elicit mesenteric ischemia in athletes. Previous studies suggest an additional 10 minute period of splanchnic hypo perfusion after discontinuation of exercise(13, 14).

The exercise test consist of 3 phases.

- Phase 1: The first 10 minutes of exercise are used to gradually increase the workload until submaximal exercise intensity is reached. Submaximal exercise is defined as lactate between 3 and 5.5 mmol/L. Lactate measurements are performed every 2 minutes, using a rapid lactate measurement kit.
- Phase 2: From minute 10 until 20 submaximal exercise intensity is maintained by adjusting the workload based on lactate measurements. The lactate measurements are performed every 3 minutes.
- Phase 3: Minute 20 until 30 are used to reach maximal exercise intensity. Every 3 minutes the workload is increased by 10% of the submaximal workload until exhaustion. Lactate measurements will be continued with 3 minute intervals.

#### *Control*

Two different control groups both consisting of 5 volunteers will be used during the study. The first group will receive  $^{13}\text{C}$ -butyrate and the second group  $^{13}\text{C}$ -glucose. The control groups will perform the breath tests without performing any physical exercise.

#### *Dosages*

All volunteers will be instructed to take their last meal 6 hours before start of the breath test. Volunteers in the  $^{13}\text{C}$ -butyrate group receive an oral dose of 0.03  $\mu\text{mol}$   $^{13}\text{C}$ -butyrate(10). Volunteers in the  $^{13}\text{C}$ -glucose group receive an oral dose of 20 mmol  $^{13}\text{C}$ -glucose(16).

### 5.2 Use of co-intervention (if applicable)

Not applicable

**5.3 Escape medication (if applicable)**

Not applicable

**6 INVESTIGATIONAL PRODUCT**

Not applicable

**6.1 Name and description of investigational product(s)**

Not applicable

**6.2 Summary of findings from non-clinical studies**

Not applicable

**6.3 Summary of findings from clinical studies**

*Not applicable*

**6.4 Summary of known and potential risks and benefits**

*Not applicable*

**6.5 Description and justification of route of administration and dosage**

Not applicable

**6.6 Dosages, dosage modifications and method of administration**

Not applicable

**6.7 Preparation and labelling of Investigational Medicinal Product**

Not applicable

**6.8 Drug accountability**

Not applicable

## 7 NON-INVESTIGATIONAL PRODUCT

### 7.1 Name and description of non-investigational product(s)

C-butyrate is a stable isotope used as a tracer molecule.

<https://www.sigmaaldrich.com/catalog/product/aldrich/488380?lang=en®ion=NL>

D-Glucose-1-C is a stable isotope used as a tracer molecule.

<https://www.sigmaaldrich.com/catalog/product/aldrich/297046?lang=en®ion=NL>

### 7.2 Summary of findings from non-clinical studies

#### *C-butyrate*

We refer to the safety information statement on the website of Sigma-Aldrich

<https://www.sigmaaldrich.com/catalog/product/aldrich/488380?lang=en®ion=NL>

#### *D-Glucose-1-C*

We refer to the safety information statement on the website of Sigma-Aldrich

<https://www.sigmaaldrich.com/catalog/product/aldrich/297046?lang=en®ion=NL>

### 7.3 Summary of findings from clinical studies

#### *C-butyrate*

A study including 12 healthy volunteers and 12 Crohn's disease patients showed that C-butyrate absorption metabolism can be measured by CO2 breath testing(17). They detected CO2 at 30 minutes after oral administration of C-butyrate, with a peak CO2 concentration at 1 hour after administration. A study showed similar results and timing of expired CO2 concentrations after instillation of C-butyrate in the cecum(10).

#### *D-Glucose-1-C*

A study including 8 healthy highly trained volunteers examined the oxidation of C-glucose during exercise(16). This study showed that CO2 could be measured reliably, in expired air, after administration of a C-glucose dose of 0.05g/kg bodyweight.

### 7.4 Summary of known and potential risks and benefits

#### *C-butyrate*

We refer to the safety information statement on the website of Sigma-Aldrich

<https://www.sigmaaldrich.com/catalog/product/aldrich/488380?lang=en®ion=NL>

### *D-Glucose-1-C*

We refer to the safety information statement on the website of Sigma-Aldrich

<https://www.sigmaaldrich.com/catalog/product/aldrich/297046?lang=en®ion=NL>

## **7.5 Description and justification of route of administration and dosage**

### *C-butyrate*

A study performing CO2 breath testing after instillation of C-butyrate in the cecum showed that a tracer dose of 0.03 μmol was sufficient and could be detected in expired air(10).

### *D-Glucose-1-C*

A study performing CO2 breath testing during exercise showed that CO2 could be measured reliably after administering an oral dose of 0.05g/kg bodyweight C-glucose(16). This dosage equals approximately 20mmol of glucose, when using a bodyweight of 70kg.

## **7.6 Dosages, dosage modifications and method of administration**

### *C-butyrate*

A study performing CO2 breath testing after instillation of C-butyrate in the cecum showed that a tracer dose of 0.03 μmol was sufficient and could be detected in expired air(10).

### *D-Glucose-1-C*

A study performing CO2 breath testing during exercise showed that CO2 could be measured reliably after administering 0.05g/kg bodyweight C-glucose(16). This dosage equals approximately 20mmol of glucose, when using a bodyweight of 70kg.

Both C-butyrate and D-Glucose-1-C are administered orally, since metabolism and absorption by the enterocytes are the processes that are of interest.

## **7.7 Preparation and labelling of Non Investigational Medicinal Product**

Preparation and labelling of the non-investigational medicinal products will be done according to the relevant GMP guidelines by licensed staff.

## **7.8 Drug accountability**

C-butyrate and D-Glucose-1-C solutions will be prepared at the Gastroenterology & Hepatology department.

## 8 METHODS

### 8.1 Study parameters/endpoints

#### 8.1.1 Main study parameter/endpoint

To explore the possibility of detecting mesenteric ischemia by  $^{13}\text{C}$ -butyrate and  $^{13}\text{C}$ -glucose breath testing by comparing timing and concentration of the peak of expired  $^{13}\text{CO}_2$ .

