Breath tests are accurate, simple and widely available tests for diseases, such as helicobacter pylori infection and small intestinal bacterial overgrowth(7, 8). Breath tests using glucose and butyrate could possibly be used to diagnose CMI. Butyrate is metabolized by the intestinal epithelium(9). Metabolism of butyrate is oxygen dependent, since oxidation is one of the steps during the production of adenosine triphosphate (ATP).  $^{14}\text{C}$ -butyrate can be used to measure the oxidation rate of butyrate(10). During the oxidation process the  $^{14}\text{C}$  atom is transferred to an oxygen molecule, producing  $^{14}\text{C}$ -carbon dioxide. The labelled carbon dioxide molecule is exhaled and can be measured in the air exhaled by the patient, thereby quantifying the presence of mucosal oxygen.

Administration of deuterated glucose ( $^{13}\text{C}$ -glucose) is a second potential method to measure mucosal oxygen content. Transport of glucose from the lumen into the epithelial cell is driven by an active process consuming ATP and thus oxygen(11). The transport of glucose is driven by a sodium gradient. At the basolateral side of the cell,  $\text{Na}^+/\text{K}^+$ -ATPase extrudes sodium, thereby creating a low sodium concentration within the cell. At the luminal side a  $\text{Na}^+$ /glucose cotransporter, driven by the low intracellular sodium concentration, transports sodium and glucose into the cell. Further transport of glucose into the mesenteric circulation occurs by diffusion facilitated by passive glucose transporters. When  $^{13}\text{C}$ -glucose is metabolized the  $^{13}\text{C}$  atom is transferred to an oxygen molecule, producing  $^{13}\text{C}$ -carbon dioxide. The labelled carbon dioxide molecule is exhaled and can be measured in the air exhaled by the patient.

In subjects with low mucosal oxygen concentrations, the peak in exhaled  $^{13}\text{CO}_2$  of butyrate and glucose is expected to be delayed and lower compared to control subjects with normal mucosal oxygen concentrations. Thereby creating a functional test measuring mucosal oxygen content, which could be of great value in diagnosing CMI.

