#### *Breath test*

Both intervention and control group will perform breath tests at the following time points baseline, 0.5, 1, 1.25 1.5, 1.75, 2, 2.25, 2.5, 3, 3.5 and 4 hours after ingestion of  $^{13}\text{C}$ -butyrate or  $^{13}\text{C}$ -glucose (figure 1). A breath sample is obtained by blowing a single breath of air through a straw into a test tube. Two breath samples are collected at all mentioned time points. The decision to perform breath testing for a total of 4 hours was based on a study that determined  $^{14}\text{CO}_2$  elimination patterns after instillation of butyrate in human caecum and a study describing  $^{13}\text{CO}_2$  elimination patterns in healthy volunteers(10, 15). The tracer could be measured in exhaled air at the first time point, which was 30 minutes after instillation. A peak in expired  $^{14}\text{CO}_2$  was measured after 2 hours. Four hours after instillation approximately 55% of the total  $^{14}\text{CO}_2$  dose had been expired, 24 hours after instillation 70% of the instilled dose had been expired. Since we are interested in the peak of expired  $^{13}\text{CO}_2$  a measurement period of 4 hours seems sufficient, even in the intervention group, in whom a delayed or lower peak is expected. The frequency of breath testing is intensified between 1 and 2.5 hours after ingestion, in order to detect the timing of the  $^{13}\text{CO}_2$  peak more precisely.

Figure 1. timeline collection of breath samples.

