## 10 STATISTICAL ANALYSIS

Baseline characteristics of the intervention and control group will be shown and compared. Categorical data is compared by chi-square or Fisher exact testing. Numerical data is shown as mean and standard deviation or median and interquartile range. Comparison of the numerical data of intervention and control group will be performed by the independent sample t-test or the Mann-Whitney-U test.

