### 10.1 Primary study parameter(s)

The height of the  $^{13}\text{CO}_2$  peak of the intervention and control groups will be compared by the independent sample t-test or Mann-Whitney-U test. Repeated measurement correction will be performed with the Bonferroni method. The area under the  $^{13}\text{CO}_2$  curves will be compared by the independent sample t-test or Mann-Whitney-U test.

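### Peak timing is a named half of the main endpoint, but section 10.1 plans comparisons only of peak height and area under the curve, and neither of these measures a delay

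*Combined protocol and SAP*

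**What the plan says.** The combined protocol and SAP has one objective and one endpoint. The Summary, section 2 and section 8.1.1 word them alike: "breath testing by comparing timing and concentration of the peak of expired" 13CO2. Secondary and other parameters are marked as not applicable in sections 8.1.2 and 8.1.3, and again in 10.2 and 10.3.

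Timing is part of the hypothesis. Section 1 says the peak "of butyrate and glucose is expected to be delayed and lower compared to control subjects with normal mucosal oxygen concentrations". The Breath test text in sections 3 and 8.3 justifies the 4-hour window "even in the intervention group, in whom a delayed or lower peak is expected", and says that sampling is closer together between 1 and 2.5 hours so that the time of the peak can be found more precisely.

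Section 10.1 plans two comparisons. The height of the "peak of the intervention and control groups will be compared by the independent sample t-test or Mann-Whitney-U test", and the area under the "curves will be compared by the independent sample t-test or Mann-Whitney-U test". Between them stands: "Repeated measurement correction will be performed with the Bonferroni method". Time to peak does not appear.

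The opening paragraph of section 10 begins "Baseline characteristics of the intervention and control group will be shown and compared" and ends "Comparison of the numerical data of intervention and control group will be performed by the independent sample t-test or the Mann-Whitney-U test".

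**The concern.** Read as written, 10.1 compares one of the two named parts of the endpoint, plus a measure that the endpoint does not name. A volunteer's peak could come later without being lower; under the 'delayed or lower' wording that would count as the expected effect, and no planned comparison would identify it.

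The breath values will exist in any case, so timing can be analysed afterwards. But its definition (how duplicates are combined, what happens with ties, what happens when the highest value is the last sample) would then be chosen with the curves in view. Section 4d also says the data may be used to size a second study; no estimate of delay is specified for that use.

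**Working it through.** **Stated figures.** 4 groups × 5 volunteers = 20 and 5 blocks × 4 = 20, which matches sections 4d and 8.2. No alpha, power, SD or effect size is given, so there is no power figure to reproduce.

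**Endpoint against analysis.**

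| Quantity | Endpoint (8.1.1) | Comparison in 10.1 |
|---|---|---|
| Time of peak | named | none |
| Height of peak | named | t-test or Mann-Whitney |
| AUC | not named | t-test or Mann-Whitney |

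**Height.** If the exercise curve is the control curve moved by d hours, f(t − d), its maximum equals that of f(t). Apart from small effects of the sampling grid, a pure delay leaves height unchanged whatever the curve shape.

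**AUC.** Take a curve (s·exp(1 − s))^k with s = t/peak time, k = 2, a 2 h peak, the protocol's 12 sampling times and the trapezoid rule. AUC over 0–4 h is 2.82. Delayed by 1 h it is 2.12, a ratio of 2.12/2.82 = 0.75. An undelayed curve at 0.75 of the height also gives 2.12. AUC cannot tell the two apart.

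**Illustrative power (assumptions, not protocol figures).** Curve h·(s/tp)^k·exp(k(1 − s/tp)) with k = 3; SD 20% of peak time and 25% of height; noise 5% of the mean control peak; 5 v 5; exact two-sided rank test at 0.05. Each pair is for a control peak at 1 h (section 7.3, oral butyrate) / 2 h (sections 3 and 8.3, butyrate instilled in the caecum). The documents give no glucose peak time. A shift moves the whole curve; a stretch lengthens it at equal height.

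| Exercise group | Time to peak % | Height % | AUC % |
|---|---|---|---|
| 0.5 h shift | 70/24 | 3/3 | 3/5 |
| 1 h shift | >99/77 | 3/3 | 3/21 |
| 0.5 h stretch | 52/19 | 3/3 | 26/4 |
| 1 h stretch | 93/55 | 4/3 | 52/3 |
| 0.5 h shift, 30% lower | 69/22 | 32/38 | 22/51 |
| 0.5 h stretch, 30% lower | 51/18 | 29/38 | 3/29 |
| 0.5 h shift, 50% lower | not needed here | 81/85 | 68/89 |

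With no effect, all three tests reject in 1–3% of trials. Over k = 2–5 and peak-time SD 10–30%, time-to-peak power for a 0.5 h delay runs from 12 to 96%.

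Mean AUC relative to control: for a 1 h peak, a shift leaves it about unchanged (0.98–1.01) and a stretch of 0.5 or 1 h raises it (1.42, 1.65). For a 2 h peak, a shift lowers it (about 0.90 for 0.5 h, 0.76 for 1 h). So the direction of the AUC change depends on the curve.

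**After correction.** For the 0.5 h shift, time to peak has about 36/8% power at 0.05/3 = 0.0167 (three measures within one tracer) and about 25/5% at 0.05/6 = 0.0083 (three measures, two tracers).

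**What Bonferroni can bear at 5 v 5.** There are C(10,5) = 252 splits. The smallest untied exact two-sided p-values are 2/252 = 0.0079, 4/252 = 0.0159 and 8/252 = 0.0317.
- Two measures (0.025) and three (0.0167): both reject at p ≤ 0.0159, so the rule is the same.
- Four tests (0.0125) and six (0.0083): both reject only at 0.0079, so the rule is the same.
- Twelve sampling times: 0.05/12 = 0.0042 < 0.0079, so no exact rank test could ever reject.

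**The case against.** The strongest defence is that timing is already committed to. Section 8.1.1 promises its comparison, so leaving it out of the report would be a visible departure, and the closing sentence of section 10's first paragraph gives a method for numerical data, which time to peak is. That reading is possible, so a reader should not infer that the plan has dropped timing or rules out analysing it. What stands is narrower: the sentence follows the one on baseline characteristics, does not name timing, does not define it, and does not say whether the correction covers it, whereas 10.1 does name height and AUC.

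A reader might also infer that the planned tests would miss the effect altogether. The documents do not support that. Section 1 expects a peak that is later and lower, and for a halved peak the height test has about 80–85% power at 0.05 under the assumptions above. With a 2 h peak that is shifted 0.5 h and 30% lower, AUC (51%) does better than time to peak (22%).

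Nor is AUC blind to a shift: it falls clearly for a 2 h peak. Equal height with a lower AUC would hint at a delay, but gives neither an estimate nor a test of it.

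The 1 h delays are also hard to tie to the documents, which describe 30 minutes of exercise and about 10 more of reduced splanchnic flow. The 0.5 h rows deserve more weight.

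Finally, this is an exploratory study of 20 volunteers without a power calculation. That limits the severity; it does not remove the mismatch.

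**Conclusion.** The point holds as a mismatch between 8.1.1 and 10.1 that should be fixed before analysis. It rests on the text and on the fact that height does not change under a pure delay; neither depends on the simulation.

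Its size cannot be fixed from the documents. Under the assumed curves, a 0.5 h shift with no lowering is found by the height test about 3% of the time. A time-to-peak test would find it about 70/24% of the time uncorrected, but only 36/8% or 25/5% after correction. Adding timing therefore supplies the missing comparison and a delay estimate; it does not make the study well powered for a delay, least of all with a peak near 2 h. No data are lost in the meantime. The risk is a definition chosen after the curves are seen, and a delay reported selectively or not at all.

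**What to change.** Add to 10.1:

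1. **Definition.** For example, time to peak per volunteer is the sampling time of the highest mean-of-duplicates 13CO2 value, with a stated rule for ties (such as the earlier time) and for a maximum at the 4 h sample (such as entered as 4 h, ranked highest, flagged as possibly not yet reached, and counted per group). Other rules would serve; what matters is that they are set in advance. Under the assumed curves, a 1 h delay from a 2 h peak puts at least one of five exercise volunteers at the 4 h sample in 26% (shift) or 50% (stretch) of trials.
2. **Comparison.** Intervention against control within each tracer, by an exact rank test that handles ties, with the difference in hours and a confidence interval.
3. **Multiplicity.** State that the Bonferroni correction is over the summary measures, including time to peak, and whether it spans both tracers, and that it is not over the 12 sampling times.
4. **Alignment.** Say what role AUC has, since 8.1.1 does not name it. Whether it stays in the corrected family is the sponsor's choice.

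**Cost.** A few sentences and no new data. The interval will be wide: on average about 0.7 h (1 h peak) or 1.5 h (2 h peak) for a 0.5 h shift. If height and AUC already share alpha and are tested by exact rank tests, they lose nothing. Otherwise height loses some power. For a 0.5 h shift with a halved peak, the exact test falls from 81 to 71% (1 h peak) and 85 to 77% (2 h peak) if it would have been tested at 0.05 and moves to 0.0167. With t-tests moving from 0.025 to 0.0167, it falls from 81 to 75% and from 85 to 80%.

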#### 8.1.2 Secondary study parameters/endpoints (if applicable)

Not applicable

#### 8.1.3 Other study parameters (if applicable)

Not applicable

### 8.2 Randomisation, blinding and treatment allocation

Participating volunteers will not be blinded. Randomization will be performed into four groups of five volunteers.

Randomisation will be performed through a random list generated by an online randomisation tool and is executed by a person not actively involved in the study. The randomisation tool can be found at <https://www.sealedenvelope.com/simple-randomiser/v1/lists>. The used seed will be noted and saved, the treatment groups are: BC, BI, GC, GI. Block sizes will be 5 blocks of 4, resulting in a randomized list of 20 subjects (5 per group). The created list will be saved and used to fill 20 envelopes numbered 1-20. Each envelope will contain the treatment group as specified in the randomly generated list. Envelope 1 will be for the first subject enrolled in the study, envelope 2 for the second subject enrolled in the study, etc.

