### 8.3 Study procedures

#### *Inclusion*

The study is conducted in healthy volunteers without gastrointestinal complaints and unremarkable medical history. Volunteers are recruited by distribution of patient information folders, containing study information and the investigators contact information, at the gastroenterology and Hepatology outpatient clinics of Erasmus MC University Medical Center and Franciscus Gasthuis & Vlietland. When volunteers contact the investigator the study outline is discussed and inclusion and exclusion criteria are checked. Volunteers are asked whether they have a medical history or are currently experiencing any complaints, they do not undergo additional tests or check-ups to ensure they are healthy. When a healthy volunteer decides to participate in the study an Informed Consent Form will be signed.

Volunteers will be randomized and assigned to one of four study groups.

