### *Randomisation*

Allocation to the  $^{13}\text{C}$ -butyrate and  $^{13}\text{C}$ -glucose group and allocation to the control or intervention group will be performed by randomisation. Blinding of the healthy volunteers will not be possible, since the intervention group has to perform an exercise test.

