#### *Analysis of breath samples*

Measurement of  $^{13}\text{CO}_2$  will be performed using mass spectrometry (IDMicro Breath, Compact Science Systems, Newcastle-Under-Lyme, United Kingdom). The mass spectrometry procedure is equal to the procedures used to measure  $^{13}\text{CO}_2$  in testing for Helicobacter Pylori, which is current clinical practice.

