**8.7 Premature termination of the study**

The study will be terminated prematurely when participation is associated with serious health risks, which are not expected.

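### Optional improvement: the printed constant block of 4 for four arms makes between 0 and 6.7 of 20 exercise/rest statuses foreseeable, depending on what the enroller knows; mixed blocks in an undisclosed order cut the upper figure to 2.7

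*Combined protocol and SAP*

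**What the plan says.** Section 8.2 names four arms, "the treatment groups are: BC, BI, GC, GI" (butyrate or glucose tracer, each as control or exercise intervention), and sets the blocking: "Block sizes will be 5 blocks of 4, resulting in a randomized list of 20 subjects (5 per group". There is one envelope series for the whole study: "Envelope 1 will be for the first subject enrolled in the study, envelope 2 for the second subject enrolled in the study, etc". The randomisation "is executed by a person not actively involved in the study", and the seed is kept.

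On visibility, section 8.3 (Randomisation) says: "Blinding of the healthy volunteers will not be possible, since the intervention group has to perform an exercise test". Whether staff are blinded is not described.

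On enrolment, section 8.3 (Inclusion) says: "When volunteers contact the investigator the study outline is discussed and inclusion and exclusion criteria are checked". Health status is established by asking, without extra tests. Volunteers are recruited through two outpatient clinics. The section places the eligibility check and consent before randomisation.

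The documents do not state who keeps or opens the envelopes, whether the enroller learns earlier allocations, whether one person enrols for both clinics, or how enrolment divides between them.

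**The concern.** With four arms and blocks of 4, each block holds every arm once, so exactly two exercise and two rest slots. The envelope number gives the position in the block. Someone who knows the block size and has seen which earlier subjects exercised can work out the status of every fourth envelope, and of the third envelope when the first two agree. Keeping the list with an independent person does not prevent this, because the information comes from what earlier subjects visibly did.

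If that person also judges eligibility by conversation, a volunteer could be accepted, postponed or discouraged with the next status in mind. Each comparison is 5 against 5, so one such volunteer is 20% of a group. The full arm can be foreseen only if earlier tracers are also known, and the exercise test does not reveal those.

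**Working it through.** **Inputs.** From section 8.2: four arms, 5 blocks of 4, 20 envelopes in enrolment order. From sections 3 and 8.3: two recruiting clinics, exercise status visible. Assumed, because the documents give no figure: the share p of subjects enrolled at one clinic, and how much the enroller knows.

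**The plan's own figure.** 5 × 4 = 20 subjects, and one of each arm per block × 5 = 5 per group. This reproduces.

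**Blocks of 4, block size or earlier allocations unknown.** Certain statuses: 0.

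**Blocks of 4, all earlier statuses known (upper bound).** Of the six equally likely exercise/rest orders in a block, two (EERR, RREE) make two slots certain and four make one slot certain.
- Certain: (2 × 2 + 4 × 1)/6 = 1.333 per block; × 5 = 6.67 of 20.
- Correct by best guessing: 1/2 + 2/3 + 2/3 + 1 = 2.833 per block; × 5 = 14.17 of 20 (71%), against 10 by chance.
- Full arm, if all earlier tracers are known too: 1 per block × 5 = 5 certain.

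**Blocks of 4, each clinic knows only its own allocations and the envelope number.** A status is certain only if the two earlier subjects who settle it were seen at the same clinic. The expected total over both clinics is (p³ + (1−p)³) × 20/3.

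| Split | Certain, both clinics together |
|---|---|
| 50/50 | (0.125 + 0.125) × 6.667 = 1.67, or 0.83 per enroller |
| 70/30 | (0.343 + 0.027) × 6.667 = 2.47 |
| 90/10 | (0.729 + 0.001) × 6.667 = 4.87 |

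An even split gives the lowest value.

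**Blocks of 4, 8 and 8, upper bound.** The three orders are taken as equally likely; the enroller knows the set of sizes but not the order.
- Correct guesses for a block of 2n: n + (4ⁿ/C(2n,n) − 1)/2. A block of 4 gives 2.833; a block of 8 gives 4 + (256/70 − 1)/2 = 5.329. Total 2.833 + 2 × 5.329 = 13.49.
- Certain: a status counts only if every order still compatible with what was seen leaves one possibility. Exact recursion over all histories gives 1.00 at envelope 20, 0.40 at envelope 19 and 1.33 over the rest, in total 2.73.
- If the order leaked: 4/3 + 2 × 8/5 = 4.53 certain.

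**One permuted list of 20, upper bound.** Certain: 2 × C(20,11)/C(20,10) = 2 × 10/11 = 1.82. Correct guesses: 10 + (4¹⁰/C(20,10) − 1)/2 = 12.34.

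**Balance during enrolment** (mean of largest minus smallest arm):

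| Enrolled | Blocks of 4 | 4/8/8, hidden order | One list of 20 |
|---|---|---|---|
| 4 | 0 | 1.03 | 1.87 |
| 8 | 0 | 0.51 | 2.29 |
| 12 | 0 | 0.51 | 2.29 |
| 16 | 0 | 1.03 | 1.87 |

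The chance of an empty arm after 8 is 0 with blocks of 4, 0 with 4/8/8, and 20.2% with one list (1.4% after 12).

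**The case against.** The strongest reply is that the whole risk is conditional. The independent person may assign as well as generate the list, and if earlier results are not passed on nothing can be foreseen. This stands, and is why the range starts at 0.

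Motive is also weak. Volunteers come forward themselves, cycling experience is required of everyone (section 4b), and workload is adjusted to lactate. The outcome is instrumental: "The mass spectrometry procedure is equal to the procedures used to measure" exhaled ¹³CO₂ in routine *Helicobacter* testing. This stands too, although objective measurement does not protect against selective enrolment.

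Blocks of 4 have a merit: exact balance after every fourth subject. Section 8.7 covers stopping for safety ("The study will be terminated prematurely when participation is associated with serious health risks, which are not expected"), but slow recruitment is not addressed, and balanced arms would then help. This is why a single list of 20 is not put forward as plainly better.

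The gain in correct guesses is small: 14.17 − 13.49 = 0.7 of 20 with 4/8/8, and 14.17 − 12.34 = 1.8 with one list. Changing block sizes also leaves open who opens the envelopes. Both points stand.

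A reader might infer that concealment is broken, that the study is biased, or that a single enroller at one clinic would foresee 1.7 allocations. The documents support none of these. They describe an independent person and numbered envelopes, show no selective enrolment, and say only that volunteers are unblinded. The 1.7 is a sum over two clinics under an assumed split.

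**Conclusion.** The point holds as an optional improvement, not as an error in the plan. A printed constant block equal to the number of arms is more predictable than this study needs: no interim analysis is planned, no stratification by centre is described, and 5 per group can be reached in other ways. The size runs from 0 to 6.7 certain statuses of 20. The upper end requires one enroller who knows the block size and every earlier exercise/rest allocation; section 8.3 does not exclude this, but does not establish it either. No effect on peak height, timing or area under the curve can be derived from the documents, and none is claimed.

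**What to change.** Before the envelopes are filled, replace the sentence on block sizes in section 8.2 with: *Blocks of mixed size (4, 8 and 8) will be used, in a random order that is not disclosed to enrolling staff; the list will be generated by the same independent person and the seed saved.* All three sizes are multiples of 4, so the list still ends at 5 per group.

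The cost is one line and a new list, plus notification as an amendment under section 12.3 if the ethics committee has already given a favourable opinion. The statistical price is the loss of exact balance at each fourth subject: a mean arm difference of about 0.5 to 1.0 at 4, 8, 12 and 16 enrolled. No arm is empty after 8, although one can be after only 4.

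One permuted list of 20 lowers predictability further (1.8 certain, 12.3 guessed in the upper case) but gives up more balance over time. Which matters more is the sponsor's choice. Either change is of use only if made before the envelopes are filled.
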